## 9.6 Discontinuation of Therapy

Reasons for permanent discontinuation include the following:

1. In patients with CIS at baseline, failure to clear CIS lesions by Week 12; however, patients who clear CIS lesions but have low-grade disease should continue to be treated. Patients with CIS lesions that fail to clear may be followed by cystoscopy until they have a cystectomy or start an alternative treatment, but will be considered non-responders in the primary efficacy analysis
2. Recurrence of high-grade papillary lesions at the Week 12 cystoscopy or later or of CIS lesions after clearance. ***Only patients who meet the definition of recurrence should be discontinued. Patients with persistence or appearance of lower grade disease should not be discontinued***
3. Unacceptable toxicity, defined as a persistent Grade 3 AE or higher despite dosing delay (according to the AE management guidelines in Section 9.5)
4. Withdrawal of consent

Any patient without tumor in the bladder but presence of tumor in the upper urinary tract will not be classified as a failure in primary analyses and will continue study participation.

The reason for early discontinuation must be documented in the electronic case report form (eCRF). After discontinuation of study treatment for any reason, patients should be followed up for 30 days to assess safety.

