#### **11.3.2 Adverse Events**

##### ***11.3.2.1 Adverse Events and Serious Adverse Events***

An AE is any untoward medical occurrence in a subject participating in a clinical trial. An AE can be any unfavorable and unintended sign, symptom, or disease temporally associated with the

use of the study medication, whether or not considered related to the study medication. AEs will be collected from the time a patient signs the ICF until 30 days after the final visit. AEs occurring prior to the start of treatment will be recorded in the eCRF and shown in listings but not in tables of AEs. Only TEAEs (ie, those AEs that begin or worsen in severity after the start of treatment) will be tabulated in the AE tables and discussed in the clinical study report.

Pre-existing, known clinically significant conditions observed at screening should be recorded as medical history. Worsening of a pre-existing condition by at least 1 grade per CTCAE version 5.0 should be recorded as an AE.

The definition of AEs also includes accidental injuries, reasons for any change in medication (drug and/or dose) other than planned titration, reasons for admission to a hospital, or reasons for surgical procedures (unless for minor elective surgery for a pre-existing condition). It also includes AEs commonly observed and AEs anticipated based on the pharmacological effect of the study medication. All new laboratory abnormalities and baseline abnormalities worsening by at least 1 CTCAE grade must be recorded as an AE when clinically significant.

A TEAE is any AE occurring after start of study medication or pre-existing medical condition that worsens in intensity after start of study medication.

AEs should be recorded as diagnoses, if available. If not available, separate sign(s) and symptom(s) are recorded. One diagnosis/symptom should be entered per record.

Note that death is not an event; however, the cause of death is. An exception is the event of sudden death of unknown cause. Note that hospitalization is not an event; however, the reason for hospitalization is. Procedures are not events; however, the reasons for conducting the procedures are. In general, only the reason for conducting the procedure will be captured as an AE. If deemed necessary by the investigator, a procedure can be captured along with the reason for conducting the procedure.

An overdose or medication error is not an AE unless it is temporally associated with an unfavorable or unintended sign or symptom.

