Not related	Another cause of the AE is most plausible, and a clinically plausible temporal sequence is inconsistent with the onset of the AE and study treatment administration and/or a causal relationship is considered biologically implausible.

AEs with the causality assessed as unlikely and not related are categorized as not related to study medication for regulatory reporting. Investigators will assess events for relationship to study medication (BC-819) and independently to study procedures (eg, catheterization for direct visualization or administration of medicine). Investigators may assess an event as possibly related to more than 1 cause.

**All SAEs must be reported immediately (no more than 24 hours after becoming aware of the event).** The investigator must complete the initial SAE Report Form and fax/e-mail it within 24 hours according to the SAE Report Form instructions. Any SAEs occurring within 30 days following study discontinuation must also be reported. The sponsor medical monitor or delegate is responsible for providing the sponsor's assessment of causality and expectedness that will be

considered when determining if the event qualifies as a serious unexpected suspected adverse reaction (SUSAR) requiring expedited reporting to regulatory authorities.

Sponsor Medical Monitor:

[name]

E-mail: [[contact]](mailto:[contact])

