### 13.6.1 Adverse Events

AEs will be coded to SOC and PT using MedDRA. All AEs occurring after the patient signs the ICF will be recorded, but only those occurring after the start of the study treatment (TEAEs) will be summarized in tables. AEs occurring between signing of the ICF and start of study medication will be included in separate listings from TEAEs.

AEs will be summarized by incidence of AEs (the number of patients reporting at least 1 episode of a specific AE), incidence of AEs by severity within body system, incidence of AEs by attribution within body system, and incidence of AEs causing withdrawal and incidence of SAEs. Regarding severity and attribution summaries, the most extreme outcome (highest severity and closest to study drug-related) will be used for those patients who experience the same AE on more than 1 occasion.

In addition to standard MedDRA SOC and PT tables of AEs, a composite class of urinary tract-related AEs will also be created and the incidence and severity of AEs in this composite class tabulated. SOC and PTs for urinary tract-related AEs are shown in [Table 13.1](#).

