7.4.1 Adverse Events

Adverse events will be graded according to the NCI CTCAE Version 5.0, coded using the MedDRA coding system, and displayed in tables and data listings by system organ class (SOC) and preferred term (PT).

A TEAE is any AE occurring after start of study medication or pre-existing medical condition that worsens in intensity after start of study medication and within 30 days of the last administration of study medication or is deemed to be related to study medication. AEs that occur after 30 days of the last administration of study medication and are not related to study medication will not be considered TEAEs.

All AEs occurring after the patient signs the ICF will be recorded, but only the TEAEs will be summarized in tables. AEs occurring between signing of the ICF and start of study medication will be included in separate listings from TEAEs.

If the start date of an AE is partially or completely missing, the date will be imputed using the rules specified in Section 7.1.3 to determine the treatment emergence. . The AE will be assumed to be treatment-emergent if it cannot be definitively shown that the AE did not occur or worsen during the treatment-emergent period (worst case approach).

Adverse events are summarized by patient incidence rates; therefore, in any tabulation, a patient contributes only once to the count for a given SOC or PT (i.e., the most related occurrence or the most intense occurrence). Missing relationship will be considered definitely related to BC-819.

An overall AE incidence summary table will be produced and will include:

- The number and percentage of patients reporting at least 1 TEAE
- The number and percentage of patients reporting at least 1 serious AE (SAE)
- The number and percentage of patients reporting at least 1 TEAE with toxicity grade of 3 or higher
- The number and percentage of patients reporting a TEAE leading to withdrawal of study drug

This document is confidential.

- The number and percentage of patients reporting a TEAE leading to study drug interruption
- The number and percentage of patients reporting a TEAE leading to death
- The number and percentage of patients reporting at least 1 TEAE related to treatment
- The number and percentage of patients reporting at least 1 treatment-related TEAE with toxicity grade of 3 or higher
- The number and percentage of patients reporting at least 1 treatment-related serious AE (SAE)

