7.7 Changes to Methods Planned in the Protocol

There are no changes from the analysis planned in the protocol.

This document is confidential.

8. Tables, Listings, And Figures

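### The SAP's 30-day limit on treatment-emergent AEs is narrower than the protocol's definition, is not declared as a change, and removes about three weeks of collected AEs not related to drug from the TEAE tables

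*SAP*

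**What the plan says.** **Protocol.** Section 11.3.2.1 gives the definition: "A TEAE is any AE occurring after start of study medication or pre-existing medical condition that worsens in intensity after start of study medication". It names no last day and asks nothing about causality. The same section fixes the collection period: "AEs will be collected from the time a patient signs the ICF until 30 days after the final visit". Section 13.6.1 says what is tabulated: of all recorded AEs, "only those occurring after the start of the study treatment (TEAEs) will be summarized in tables". For causality, section 11.3.2.2 says "Investigators will assess events for relationship to study medication (BC-819) and independently to study procedures".

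**SAP.** Section 7.4.1 starts from the protocol definition. It then requires onset within 30 days of the last instillation or a relationship to study medication, and makes the exclusion explicit: "AEs that occur after 30 days of the last administration of study medication and are not related to study medication will not be considered TEAEs". It adds that only TEAEs go into tables. Section 5.2 defines the safety endpoint as TEAEs whatever their relationship to drug. Section 7.7 states: "There are no changes from the analysis planned in the protocol".

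**The concern.** Safety is a stated objective, and the AE tables are its main result. The two documents define different sets of events for those tables, and the SAP says they agree. The SAP's condition also sits badly with its own endpoint: after day 30, causality decides whether an event counts.

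The exemption covers relationship to drug only. A late event that the investigator attributes to catheterization, biopsy or resection, and not to BC-819, does not meet it. Such events matter here. Urinary tract infection, urosepsis and all renal and urinary disorders form a planned composite (Protocol Table 13.1), and Protocol 7.3 reports urinary events in earlier studies that were attributed wholly or partly to procedures. In an open-label single-arm trial, an unblinded causality rating would then settle whether a late event is tabulated.

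**Working it through.** The plan states no figure for this gap, so there is none to reproduce. The check is day arithmetic on the schedule.

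**Inputs**
- Last induction dose Day 64 (Visit 10, Protocol Table 12.1); Week 12 visit Day 84 (Table 12.2).
- Last maintenance dose Week 93 (Visit 38); final visit Week 96 without treatment (Visit 39; Protocol 9.4.3 and Table 12.3). Counting 7 days per week: 93 × 7 = Day 651 and 96 × 7 = Day 672.
- SAP window: last dose + 30 days. Protocol collection: final visit + 30 days.
- Cystoscopy and cytology: within the 14 days before the visit (Protocol 9.4.3 and 12).
- End-of-study procedures: up to 4 weeks after leaving (Protocol 12).

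**Collected days outside the SAP window**

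Gap = (final visit + 30) − (last dose + 30) = final visit − last dose.
- Week 12 failure whose final visit is Week 12: the window closes on Day 64 + 30 = 94 and collection on Day 84 + 30 = 114. Gap 114 − 94 = 20 days (Days 95 to 114).
- Completer: the window closes on Day 651 + 30 = 681 and collection on Day 672 + 30 = 702. Gap 702 − 681 = 21 days (Days 682 to 702).
- Week 12 failure with end-of-study procedures the full 4 weeks later (assumption): 84 + 28 + 30 = Day 142. Gap 142 − 94 = 48 days.
- Week 12 failure with follow-up counted 30 days from the last dose (one reading of Protocol 9.6): 64 + 30 = Day 94. Gap 0 days.

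**What the SAP window still covers after the assessment**
- Week 12: cystoscopy on Days 70 to 84. Days left to Day 94: 94 − 84 = 10 to 94 − 70 = 24.
- Week 96: cystoscopy on Days 658 to 672. Days left to Day 681: 681 − 672 = 9 to 681 − 658 = 23.

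So 9 to 24 days after an on-schedule cystoscopy are tabulated whatever the causality.

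**Which events leave the TEAE tables**

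Only events in the gap that are rated not related to drug. I assume that the SAP groups causality as Protocol 11.3.2.2 does for regulatory reporting, with the two lowest categories (unlikely, not related) counted as not related; SAP 7.4.1 does not state the grouping. Missing relationship is set to definitely related, so those events stay in.

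**The case against.** A limit of 30 days after the last dose, waived for drug-related events, is a defensible main definition. Week 12 failures may go on to cystectomy or another treatment. Without a limit, unrelated events that follow those treatments but fall within the collection period would be tabulated as BC-819 TEAEs. This stands as a reason to show both versions. It does not excuse an undeclared departure from the protocol.

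Protocol 9.6 says: "After discontinuation of study treatment for any reason, patients should be followed up for 30 days to assess safety". Counted from the last dose, this matches the SAP window for patients who stop early. But section 11.3.2.1 ties AE collection to the final visit, and section 11.3.2.2 adds: "Any SAEs occurring within 30 days following study discontinuation must also be reported". The protocol thus uses three anchors, so the gap for early stoppers depends on which one sites follow.

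Three stronger readings are tempting, and the documents do not support them.
- A reader might infer that late events vanish from every safety table. On-study AEs are listed and SAEs have their own listing (SAP 7.4.1). Deaths also appear in disposition (SAP 7.2.1) and in the efficacy summaries (SAP 7.3.2.1). The SAE rows and tables are not labelled treatment-emergent, although the same section says that only TEAEs are tabulated. For SAEs the text is ambiguous; it does not clearly exclude them.
- A reader might infer that a urosepsis or bleed after the Week 12 or Week 96 cystoscopy would go untabulated. Within the 9 to 24 days shown above it is a TEAE. Only later onset, or a delayed biopsy, resection or end-of-study procedure, falls outside.
- A reader might take the complement of the 35% to 40% design response rate as the number affected at Week 12: 70 × 0.60 = 42 to 100 × 0.65 = 65 patients. That rate is response at any time from Week 12 to Week 48 (Protocol 11.1), and Table 12.2 schedules later assessments for patients without an earlier response. It does not count patients who stop at Week 12, still less lost events.

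**Conclusion.** The point stands as an undeclared difference of definition with a bounded effect. Followed as written, the SAP removes from the TEAE tables about 20 days (Week 12 failure) to 21 days (completer) of collected AEs rated not related to drug, including those related only to a procedure. The statement in SAP 7.7 is wrong on this item.

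The size assumes on-schedule visits, collection to 30 days after the final visit, and a final visit at Week 12 or Week 96. It rises to 48 days for a Week 12 failure whose end-of-study procedures come 4 weeks later. It could be longer if continued cystoscopic follow-up of patients whose CIS has not cleared (Protocol 9.6 and 13.3) postpones the final visit. It falls to zero for early stoppers if Protocol 9.6 is counted from the last dose.

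The documents give no late-event rate, so the number of AEs affected cannot be computed. The direction is towards lower tabulated incidence, tempered by the rules that keep drug-related and missing-relationship events in.

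**What to change.** Either of two changes to SAP 7.4.1 resolves this.

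1. Preferred: use the protocol definition for the main TEAE tables, so that every AE starting or worsening after the first instillation, through the end of AE collection, is included. Keep the version limited to 30 days or drug-related events as a supplementary set.
2. Otherwise: keep the 30-day window as the main definition, declare it in SAP 7.7, extend the exemption to procedure-related AEs, and state that all SAEs and deaths in the collection period are tabulated regardless of the window.

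Under either option, the SAP should say which rule governs the SAE rows and tables, and how the five causality categories are grouped. The follow-up anchors in Protocol 9.6, 11.3.2.1 and 11.3.2.2 should be reconciled so that the end of collection is unambiguous.

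The cost is SAP wording and extra tables from data already collected. Reported AE incidence may rise slightly, and option 1 may count some events after subsequent treatment. The supplementary tables would show how much of the total these make up.

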No dose-limiting toxicities were observed or reported, and no deaths occurred during the study or during the follow-up period. Intravesical administration of BC-819 at doses from 2 mg to 20 mg plasmid weekly for 6 weeks was well tolerated. The most frequently reported AEs considered to be at least possibly related to investigational product for any dose cohort were mild to moderate in severity and were most commonly renal and urinary disorders. Mild bladder discomfort and dysuria were reported in 11.1% and 16.7% of patients, respectively. Moderate dysuria and micturition urgency were reported in 5.6 % and 16.7% of patients, respectively. Severe (Grade 3) micturition urgency was reported by 1 patient in the 6-mg dose cohort after the fourth intravesical treatment. In total, 44% of patients had a urinary tract infection during the study, of which 17% were considered related to other investigational procedures such as the video-cystoscopy, catheterization, or surgical resection. Mild (Grade 1) diarrhea, hypertension, and asthenia were reported in 11.1%, 16.7 %, and 11.1% of patients, respectively. Laboratory AEs considered possibly related to treatment included increased blood creatinine and leukopenia in 22.2% and 11.1% of patients, respectively. There was no dose-response relationship in overall AEs (related + nonrelated). One serious adverse event (SAE) considered possibly related to study treatment, urinary urgency requiring hospitalization, occurred in the study. This SAE occurred in a patient in the 6-mg weekly treatment group.

The primary efficacy assessment was overall response rate (complete and partial) as directly visualized by cystoscopy at Week 12; in 4 of 18 patients (22%), complete responses were observed. In an additional 4 of 18 patients (22%), partial responses were observed. Thus, total responses were observed in 8 of 18 patients (44%). Median time to recurrence among all 18 study patients and across all dosing levels was 5.7 months (95% CI was 4.1 to 11.6 months).

H19 expression was detected in all tumors at baseline. 12/18 (66.7%) of the patients were recurrence-free at 3 months, and 44.4% and 33.3% were recurrence-free at 12 months and 24 months respectively.

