The most commonly reported AEs were renal and urinary disorders, experienced by 30% of patients entered. These included urinary frequency (15%), dysuria (11%), micturition urgency (6%), and urinary retention (6%). Urinary tract infections, classified under infections and infestations, were reported by 11% of patients. Other AEs experienced by 3 or more patients included increased blood potassium (11%) and asthenia, chills, pyrexia, and nausea (6%, each). No patients had an elevation of either creatinine or blood urea nitrogen levels.

Seven SAEs in 5 patients were reported: 1 patient developed urinary retention and a urinary tract infection and subsequently underwent TUR of the prostate; 1 patient developed a myocardial infarction; 1 patient developed hematuria; 1 patient developed pneumonia; and 1 patient had an exacerbation of pre-existing chronic obstructive pulmonary disease. Only the event of hematuria was considered by the treating investigator to be possibly related to study treatment, though also probably related to study procedure. SAEs in the other 4 patients were considered unrelated to study medication or procedure; 2 patients were screen failures who never received any study drug.

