### **9.3.2 Exclusion Criteria**

The presence of any of the following excludes a patient from study enrollment:

1. Patient has current or previous evidence of muscle invasive (muscularis propria) or metastatic bladder cancer disease
2. Patient has received prior investigational therapy for NMIBC
3. Patient has received any therapy for NMIBC within 10 weeks before the start of study treatment other than surgical resection, 1 dose of chemotherapy, and previous BCG
4. Patient is intolerant to previous BCG treatment in the absence of meeting other criteria for BCG unresponsiveness and adequate BCG therapy
5. Patient has received external beam radiation therapy for bladder cancer at any time or for any other condition
6. Patient has an active infection, including urinary tract infection (viral, bacterial, or fungal) and cystitis
7. Patient has urinary tract signs or symptoms that preclude retention of drug in the bladder; this does not include anticholinergic drugs
8. Patient is known to have tested positive for human immunodeficiency virus (HIV). No HIV testing is required if patient is not known to have tested positive

9. Patient is female and is pregnant or breastfeeding
10. Patient has any medical, psychological, or social condition or situation that may, in the investigator's opinion, make it difficult for the patient to tolerate study medication or comply with study procedures and other requirements. This includes but is not limited to active infections, poorly controlled diabetes, uncontrolled cardiac arrhythmia, angina pectoris, or hypertension
11. Patient has a known presence or history of malignancy of other organ system within the 5 years before study start, with the exception of non-melanoma skin cancer (eg, basal cell carcinoma or squamous cell carcinoma of the skin); very low or low-risk prostate cancer (by National Comprehensive Cancer Network guidelines) defined as prostate-specific antigen <10 ng/dL, Gleason score ≤6, and clinical stage T1c; or patients who have been disease-free for at least 2 years following stage 1 or 2 cancer
12. Patient is on immunosuppressive therapy or has had a transplant within 12 months before study start, except for chronic use of corticosteroids (eg, rheumatoid arthritis, asthma, chronic obstructive pulmonary disease, or any other similarly chronic use of steroids)
13. Patient has any other significant disease that, in the opinion of the investigator, would prevent study entry

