- The number and percentage of patients reporting a treatment-related TEAE leading to death

Tabulations by SOC and PT will be produced for all TEAEs, treatment-related TEAEs, SAEs, treatment-related SAEs, TEAEs Grade ≥ 3 (including columns for highest grade 3, 4, and 5), treatment-related TEAEs Grade ≥ 3 (including columns for highest grade 3, 4, and 5), TEAEs leading to study drug withdrawal, TEAEs leading to study drug interruption, treatment-related TEAEs leading to death and TEAEs, treatment-related TEAEs and SAEs by maximum toxicity grade. These will be presented by SOC and PT, sorted by decreasing frequency. The tabulations will be also be presented separately by PT, sort by decreasing frequency. All tabulations will be presented by overall patients. Additionally, overall summary, TEAEs, treatment-related TEAEs, TEAEs Grade ≥ 3 , treatment-related TEAEs Grade ≥ 3 , SAE, treatment-related SAE, treatment-related death will also be tabulated by patients with baseline CIS.

In addition to standard MedDRA SOC and PT tables of AEs, a composite class of urinary tract-related AEs will also be created and the incidence and severity of AEs in this composite class tabulated. SOC and PTs for urinary tract-related AEs are shown in Table 4.

Table 4 Urinary Tract–Related Adverse Events

System Organ Class	Preferred Term
Infections and infestations	Urinary tract infection
	Urosepsis
Investigations	Blood creatinine increased
Renal and urinary disorders	Any

No formal hypothesis-testing analysis of AE incidence rates will be performed. All AEs occurring on-study will be provided in data listings. By-patient listings also will be provided for the following: SAEs, AEs leading to study drug withdrawal, and AEs leading to study drug interruption.

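### The urinary tract-related AE composite takes only two preferred terms from 'Infections and infestations', so a urinary infection coded to any other term in that class is not counted

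*SAP*

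**What the plan says.** Both documents plan a composite safety class that cuts across SOCs. In SAP 7.4.1, "a composite class of urinary tract-related AEs will also be created and the incidence and severity of AEs in this composite class tabulated". Protocol 13.6.1 plans the same and fixes membership by a table: "SOC and PTs for urinary tract-related AEs are shown in" Table 13.1. The SAP's table (the one numbered 4 in section 7.4.1) has the same rows:

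- Infections and infestations: 'Urinary tract infection' and 'Urosepsis'.
- Investigations: 'Blood creatinine increased'.
- Renal and urinary disorders: any PT.

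Neither document adds a grouped term, open-ended wording or a medical-review step that would bring in further infection terms.

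Three other places bear on how urinary infections may be recorded:

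- Protocol 11.3.2.1, on recording: "AEs should be recorded as diagnoses, if available".
- Protocol 9.3.2, criterion 6, which names two conditions side by side: "Patient has an active infection, including urinary tract infection (viral, bacterial, or fungal) and cystitis".
- Protocol 7.3.2, on the earlier Phase 2 monotherapy study: "Urinary tract infections, classified under infections and infestations, were reported by 11% of patients".

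**The concern.** The table treats its two main classes differently. A disorder coded to 'Renal and urinary disorders' always counts. An infection counts only if it is coded to one of two named PTs.

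The protocol asks for diagnoses, and its own vocabulary for active urinary infection goes beyond the listed terms, since cystitis is named beside urinary tract infection. A site could therefore report a specific diagnosis that the dictionary places in 'Infections and infestations' under another PT. The plan, followed exactly, would leave that event out of the summary meant to collect urinary harm.

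At stake is the completeness of one descriptive safety table. Efficacy conclusions and decisions during the trial are not affected.

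**Working it through.** The plan states no figure for the composite, so there is none to reproduce. The check reads the rule against the possible codings and then sizes a single omission.

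**Step 1. Where a urinary infection can go.**

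| Coding of the event | In the composite? |
|---|---|
| 'Urinary tract infection' or 'Urosepsis' | Yes, named |
| Any PT in 'Renal and urinary disorders' | Yes, through the 'Any' row |
| Another PT in 'Infections and infestations' | No |

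The documents do not say how often the third case will arise. Protocol 7.3.2 places the earlier urinary tract infections in 'Infections and infestations', so the restricted row is the relevant one for infections.

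**Step 2. What an omission does to one patient.**

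- No other listed event: the patient is missing from the incidence.
- A listed event of lower grade (say Grade 1, with an omitted Grade 3 infection): the patient is counted, but at Grade 1.
- A listed event of equal or higher grade: neither incidence nor maximum grade changes.

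**Step 3. Size.** Safety is analysed in the full analysis set, planned at N = 140 (SAP 7.1.5 and 7.4). With k the number of patients in the first situation:

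loss in incidence = k / 140

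- k = 0: 0 points
- k = 1: 1/140 = 0.71 points
- k = 2: 2/140 = 1.43 points
- k = 5: 5/140 = 3.57 points

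The values of k are assumptions that show the scale. Nothing in the documents predicts k.

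**Step 4. Whether another planned table gives the same number.** SAP 7.4.1 counts a patient once per SOC or PT. Adding PT rows would count a patient with two urinary events twice. The 'Renal and urinary disorders' row gives a patient-level figure for that class only, and the 'Infections and infestations' row mixes in infections outside the urinary tract. No other planned table gives patient-level urinary incidence and severity across classes. It would have to be counted by hand from the listings.

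**The case against.** The case against has real weight.

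- **The premise is not shown.** No text demonstrates a urinary infection coded to an unlisted PT. Criterion 6 is eligibility wording and sets no coding rule. Cystitis after instillation might well be coded to 'Renal and urinary disorders' and be counted. This stands, and it is why the size may be zero.
- **Nothing is hidden.** All treatment-emergent events are tabulated by SOC and PT, by PT alone and by maximum grade, with Grade ≥3 and serious-event tables and full listings. Protocol 13.6.1 also promises narratives for serious or otherwise significant events of special interest. This stands.
- **The definition is prespecified and the same in both documents.** True, but a transparent closed list can still be narrower than its purpose.
- **The repair is one-sided.** The creatinine row counts an increase whatever its cause. Phase 1 reported "increased blood creatinine and leukopenia in 22.2% and 11.1% of patients, respectively" as possibly related laboratory events, whereas in Phase 2 "No patients had an elevation of either creatinine or blood urea nitrogen levels". The creatinine and 'Any' rows may overcount. This also stands, but those rows concern different events and do not put back an omitted infection.

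Two stronger readings are tempting. The first would size the loss by applying an assumed missed share to the earlier infection rates: 11% in Phase 2, and in Phase 1 "In total, 44% of patients had a urinary tract infection during the study" (18 patients treated). Those are reported rates of urinary tract infection, which is the listed term. Read that way, such patients are captured, and the unlisted share is not given anywhere. The second would quote 1/35 = 2.9 points for the futility look. The interim outputs in SAP 7.5 and Appendix 10.1 do not include the composite. That figure would arise only if the study stopped at 35 patients and a final composite table were then produced.

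**Conclusion.** The point holds as a minor one. By its own rule, the composite omits any urinary infection coded to a PT in 'Infections and infestations' other than the two named. It can therefore undercount patients or understate maximum grade.

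The effect is 0.7 percentage points for each missed patient with no other listed event, assuming all 140 planned patients are treated. The number of such patients is unknown and may be none.

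A reader might infer that the composite as a whole is biased low. The documents do not support that, because other rows may count events that are not urinary-tract harm and the net direction is unknown. Nor do they support any claim that the primary endpoint, the interim rule or dosing is affected. This is a cheap improvement to descriptive reporting.

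**What to change.** In the SAP 7.4.1 table, replace the two-term 'Infections and infestations' entry with: 'Urosepsis, and all PTs that the MedDRA version used for coding groups as urinary tract infections'.

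- Fix the list from the dictionary hierarchy before the analysis, without reference to the events observed. This matters in an open-label, single-arm study.
- Tie the list to the version actually used, since SAP 7.1.1 allows version 21.0 or later, and check that both current terms remain in it.
- Report the present two-term definition as a secondary row. If no event is coded elsewhere, the two rows will agree.
- Record the change in SAP 7.7, which now states that there are none, and align Protocol Table 13.1 if the protocol is next amended.

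The cost is one term list, one table row and the document entries. No new data are needed, because MedDRA coding is already planned. The reported composite rate may be slightly higher. Possible overcounting through the creatinine and 'Any' rows is not addressed.
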